20.9.1 Summaries / analyses of PFS

- Based on the FAS and IRC
- Based on the FAS and the investigator tumor response assessment (INV)
- Based on the ITT and IRC

-
- Based on the ITT and the investigator tumor response assessment (INV)

Kaplan-Meier graphs will be produced for each combination.

20.9.2 Summaries / analyses of DoR

- Based on the FAS and IRC
- Based on the FAS and the investigator tumor response assessment (INV)
- Based on the ITT and IRC
- Based on the ITT and the investigator tumor response assessment (INV)

Kaplan-Meier graphs will be produced for all summary Tables.

20.10 First line treatment category

Summary

The number (%) of patients who received a first-line treatment belonging to the following categories will be tabulated:

- Number (%) of patients treated with R-CHOP
- Number (%) of patients treated with R-CHOP equivalent regimens
- Number (%) of patients treated with non-R-CHOP regimens

Based on the 'prior cancer therapies for DLBCL medication' eCRF page, the following strategy will be applied to find out whether a first-line treatment belongs to one of the categories mentioned above. The information on the first line treatment can be reported in the eCRF in several ways:

- One acronym in a single eCRF log line (e.g., "R-CHOP")
- Individual components of a regimen entered in a single eCRF log line (e.g., one log line with entry: "rituximab, cyclophosphamide, hydroxydaunorubicin, vincristine, prednisone")
- Individual components of a regimen entered across multiple eCRF log lines

The case (small or capital letter) will be ignored during screening. In case a regimen is reported as individual components, the regimen will only be considered as R-CHOP or R-CHOP equivalent if all components belonging to the regimen are present (regardless of any additional drugs that have been co-administered). Multiple search terms for a particular drug will be applied to cover generic and grand names. Both the verbatim terms as entered by the investigator as well as the coded terms will be screened. The following search terms will be used

Treatment category assignment	Search terms used to identify regimens belonging to the treatment category of interest	Search terms used to identify regimen components indicating a particular treatment category (R-CHOP vs. R-CHOP equivalent vs. Other)
R-CHOP	
 • “R-CHOP” or “RCHOP” or “R CHOP” • “R-mini-CHOP” or “R mini-CHOP” • “R-CHOP14” or “RCHOP14” or “R CHOP14” • “Pola-R-CHP” 	
(“rituximab” or “rtx”) and “cyclophos” and “prednis” and “vincris” or “leurocris” or “vcr”)
 
OR:
 
“CHOP” and (“rituximab” or “rtx”)
 
OR:
 
“CHP” and (“pola” or “polivy” or “CD79” and (“rtx” or “rituximab”)
 
OR:
 
“RCHP or R-CHP” and (“pola” or “polivy” or “CD79”)

R-CHOP equivalent	
 • “R-ACVBP” or “RACVBP” or “R ACVBP” • “R-CHOEP” or “RCHOEP” or “R CHOEP” • “R-EPOCH” or “REPOCH” or “R EPOCH” • “R-HyperCVAD” or “R HyperCVAD” • “DA-R-EPOCH” or “R- 	
(“rtx” or “rituximab” or “obinu” or “GA101” or “polivy” or “pola” or “CD79”) and “ACVBP”
 
OR
 
(“rtx” or “rituximab” or “obinu” or “GA101” or “polivy” or “pola” or “CD79”) and (CHOEP or CHOP)

STATISTICAL ANALYSIS PLAN

 MorphoSys AG
 MOR208C203

	EPOCH" or "R-DA-EPOCH" or "R DAEPOCH" or "R EPOCH" 
 • "G-CHOP" or "GCHOP" or "G CHOP" • "G-mini-CHOP" or "G mini-CHOP" • "GA101-CHOP" or "GA101 CHOP" 	("rtx" or "rituximab" or "obinu" or "GA101" or "polivy" or "pola" or "CD79") and EPOCH
--	---	--

If a patient cannot be classified as having been treated with an R-CHOP or R-CHOP equivalent regimen, the patient will be classified as having received a non-R-CHOP treatment.

Listing

A Listing will be provided showing the first line treatment by the following categories:

- Number (%) of patients treated with R-CHOP
- Number (%) of patients treated with R-CHOP equivalent regimens
- Number (%) of patients treated with non-R-CHOP regimens

The Listing will display the following:

- All components of the first-line regimen as reported verbatim in the eCRF
- The coded terms of the regimen / components
- The start date for all regimen components
- The stop date for all regimen components

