GEP	Gene expression profiling
GGT	Gamma-glutamyltransferase
GLP	Good laboratory practice
HbsAg	Hepatitis B surface antigen
HBV	Hepatitis B virus
HCL	Hairy cell leukaemia
HCV	Hepatitis C virus
HDC	High-dose chemotherapy
HIV	Human immunodeficiency virus
IB	Investigator's brochure
ICE	Ifosfamide, carboplatin, etoposide
ICF	Informed consent form
ICH	International Conference on Harmonisation
ICMJE	International Committee of Medical Journal Editors
IEC	Independent ethics committee
Ig	Immunoglobulin
IHC	Immunohistochemistry
IIT	Investigator initiated trial
IL-2	Interleukin-2
IMiD [®]	Immunomodulatory drug
IMP	Investigational medicinal product
IND	Investigational new drug
iNHL	Indolent non-Hodgkin lymphoma
IPI	International Prognostic Index
IRB	Institutional/independent review board
IRR	Infusion-related reaction
IV	Intravenous
IWG	International Working Group
LDH	Lactate dehydrogenase
LEN	Lenalidomide
mAb	Monoclonal antibody
MALT	Mucosa-associated lymphoid tissue lymphoma
MCL	Mantle cell lymphoma
MedDRA	Medical Dictionary for Regulatory Activities
MM	Multiple myeloma
MRI	Magnetic resonance imaging
MTD	Maximum tolerated dose
MYC	v-myc avian myelocytomatisis viral oncogene homolog
MZL	Marginal zone lymphoma

NCI	National Cancer Institute
NHL	Non-Hodgkin lymphoma
NK	Natural killer
NOAKs	New oral anticoagulants
NOS	Not otherwise specified
NSAIDs	Non-steroidal anti-inflammatory drugs
NYHA	New York Heart Association
ORR	Objective response rate (complete response + partial response)
OS	Overall survival
PD	Pharmacodynamics
PE	Physical examination
PET	Positron emission tomography
PFS	Progression-free survival
PK	Pharmacokinetic
PLL	Prolymphocytic leukaemia
PMBL	Primary mediastinal (thymic) large B-cell lymphoma
p.o.	By mouth
PPS	Per-protocol set
PR	Partial response
PR (ECG)	PR interval
PT	Preferred term
QRS	QRS interval
QT	QT interval
RBC	Red blood cell
R-CHOP	Rituximab plus cyclophosphamide, hydroxydaunorubicin (also referred to as doxorubicin or adriamycin), and oncovin (vincristine) plus prednisone or prednisolone
REAL/WHO	Revised European American Lymphoma/World Health Organization
R-EPOCH	Rituximab plus etoposide, prednisone or prednisolone, oncovin, cyclophosphamide, and hydroxydaunorubicin
R-ICE	Rituximab plus ifosfamide, carboplatin, etoposide
RNA	Ribonucleic acid
rpm	Respirations per minute (respiration rate)
RR (ECG)	RR interval
R-R	Relapsed or refractory
R-R CLL/SLL	Relapsed or refractory chronic lymphocytic leukaemia/small lymphocytic lymphoma

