1.2 Treatment of DLBCL

DLBCL is considered to be a chemosensitive neoplasm. Originally, CHOP (cyclophosphamide, doxorubicin, vincristine, and prednisone) chemotherapy was the standard first-line treatment. However the addition of rituximab (RTX) into CHOP-like (R-CHOP-like), anthracycline-based regimens has significantly improved the clinical results in patients with DLBCL, becoming the standard of care ([Feugier et al., 2005](#); [Habermann et al., 2006](#); [Coiffier et al., 2002](#)).

Nevertheless, even with the availability of R-CHOP-like treatment regimens, approximately 30–40% of patients will ultimately relapse or progress. In patients progressing or relapsing after first-line treatment the ultimate therapeutic goal is to be able to offer salvage chemotherapy such as DHAP (cisplatin, cytarabine, dexamethasone), VIM (etoposide, ifosfamide, methotrexate), ICE (ifosfamide, carboplatin, etoposide), or ESHAP (etoposide, methylprednisolone, cytarabine, cisplatin), followed by high-dose chemotherapy (HDC) with autologous stem cell transplantation (ASCT) if the disease is still chemosensitive. HDC with ASCT is a potentially curative treatment, significantly improving disease-free survival and overall survival (OS) in patients with relapsed DLBCL ([Philip et al., 1995](#)).

However, the use of HDC with stem cell support may not be appropriate, especially for patients with comorbidities or older age, restricting the benefit of this aggressive approach to a relatively small percentage of patients. For the remaining patient population, several second-line combination therapies are used with variable success, but the median survival for patients who

have relapsed after second-line therapy is less than one year, and the median survival for those not responding to second-line therapy is less than 6 months.

Monoclonal antibody (mAb) therapy may have the potential to improve objective response rates (ORRs) and OS without increasing haematological toxicity. This is supported by data from studies investigating other CD19 mAbs, including MDX-1342, SAR3419 and MEDI-551 ([Ribrag et al., 2014](#); [Matlawska-Wasowska et al., 2013](#); [Younes et al., 2012](#); [Bargou et al., 2008](#); [Viardot et al., 2011](#)).

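### SAP 20.10: the drug-name search for R-CHOP has no anthracycline term, and its categories overlap, so the first-line treatment table can be wrong as programmed

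*SAP*

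**What the plan says.** SAP 20.10 (Addendum 5.0) tabulates first-line treatment in three categories from the eCRF page on prior DLBCL medication. It expects three styles of entry: an acronym, all drugs on one log line, or drugs spread over several log lines. For entries by drug, "the regimen will only be considered as R-CHOP or R-CHOP equivalent if all components belonging to the regimen are present", and this holds "regardless of any additional drugs that have been co-administered". The section's own sample of such an entry is "rituximab, cyclophosphamide, hydroxydaunorubicin, vincristine, prednisone".

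The search table then gives the R-CHOP drug-name string: rituximab or `rtx`, followed by "cyclophos” and “prednis” and “vincris” or “leurocris” or “vcr". A second R-CHOP rule accepts `CHOP` with rituximab.

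In the equivalent row, the component column pairs an antibody term with a backbone acronym (ACVBP, CHOEP, CHOP or EPOCH). One of these rules ends "CD79”) and (CHOEP or CHOP", and rituximab is among its antibody terms. A patient matched by neither row is non-R-CHOP.

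The Protocol's abbreviation list defines R-CHOP as "Rituximab plus cyclophosphamide, hydroxydaunorubicin (also referred to as doxorubicin or adriamycin), and oncovin (vincristine) plus prednisone or prednisolone" and R-EPOCH as "Rituximab plus etoposide, prednisone or prednisolone, oncovin, cyclophosphamide, and hydroxydaunorubicin". Protocol 1.2 describes "CHOP (cyclophosphamide, doxorubicin, vincristine, and prednisone) chemotherapy".

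**The concern.** The section states one rule and supplies search terms that implement another. The search terms are what gets programmed. The table is meant to show how many patients had R-CHOP or a comparable regimen first line. A reader of a single-arm trial uses that to judge how the enrolled population resembles others. If a regimen without an anthracycline can be counted as R-CHOP, or if the label depends on how a site typed the same regimen, the table does not report what its row names say. Because one common style of entry satisfies two rows, two programmers following the text could also produce different tables.

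**Working it through.** There is no plan figure to reproduce, so the check applies the search rules as written to test entries.

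**Rules, from SAP 20.10.** Matching ignores case and looks for substrings. The vincristine alternatives are first read as one group.

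- R-CHOP by drug name: (rituximab or rtx) and cyclophos and prednis and (vincris or leurocris or vcr).
- R-CHOP by backbone: `CHOP` and (rituximab or rtx). There are also two `CHP` rules that need a polatuzumab/CD79 term.
- Equivalent: a listed acronym, or any of (rtx, rituximab, obinu, GA101, polivy, pola, CD79) with ACVBP, CHOEP, CHOP or EPOCH.
- Otherwise: non-R-CHOP.

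**Results.** The last column adds a required anthracycline term to the R-CHOP drug-name rule and changes nothing else.

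| Entry | R-CHOP row | Equivalent row | Label as written | With anthracycline term |
|---|---|---|---|---|
| SAP's sample entry (five drugs) | match | no | R-CHOP | R-CHOP |
| Same entry without hydroxydaunorubicin | match | no | R-CHOP | non-R-CHOP |
| `R-CVP`, or rituximab with `CVP` | no | no | non-R-CHOP | non-R-CHOP |
| R-EPOCH as six drug names | match | no | R-CHOP | R-CHOP |
| `R-EPOCH`, or rituximab with `EPOCH` | no | match | equivalent | equivalent |
| Rituximab with `CHOP` | match | match | undetermined | undetermined |
| Obinutuzumab plus the CHOP drugs by name | no | no | non-R-CHOP | non-R-CHOP |
| `G-CHOP` | no | match | equivalent | equivalent |

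**Reading the rows.**

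1. Rows 1 and 2 get the same label, although only row 1 meets the stated all-components rule. The string contradicts the prose.
2. Rows 4 and 5 are the same regimen with different labels. By the Protocol's definition R-EPOCH is the R-CHOP drugs plus etoposide. The equivalent row has no individual chemotherapy names, so a drug list cannot match it, and the added etoposide is ignored by rule. Requiring an anthracycline does not change this.
3. Row 6 meets both rows, and no order of testing is given.
4. Rows 7 and 8 show the same dependence on typing in the other direction: a listed equivalent falls to non-R-CHOP.
5. The drug-name string closes a parenthesis that it never opened before the vincristine alternatives. Under the usual precedence (and before or), `leurocris` or `vcr` alone would be enough. An entry of ifosfamide and vcr would then be R-CHOP.

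**Size.** SAP 20.10 names no analysis set, so the planned enrolment of about 80 is used. The shift in a category for k misclassified patients is k × 100/80, that is 1/80 = 1.25 percentage points for each patient. Neither document gives regimen frequencies, so k is unknown and can be 0.

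- Row 2 raises R-CHOP, and the combined R-CHOP plus equivalent share, by 1.25 points per patient.
- Row 4 raises R-CHOP by 1.25 and lowers equivalent by 1.25. The combined share changes by 0.
- Row 7 lowers the combined share by 1.25 points per patient.

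**The case against.** The prose rule is correct and would exclude a four-drug regimen without an anthracycline, so this is a coding slip rather than a wrong analytic choice. That is a fair description. But the section says that the listed terms will be used, and nothing tells the programmer to let the prose override them.

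The unbalanced parenthesis could mean that table text, perhaps a doxorubicin term, was lost when the PDF was read. This cannot be fully excluded. The `CHP` string in the same cell is unbalanced too, which points to drafting in the source. The rituximab-with-`CHOP` overlap and the lack of drug names in the equivalent row do not depend on that string.

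Ignoring co-administered drugs is an explicit convention, and labelling R-CHOP plus etoposide as R-CHOP follows from it. That stands as far as it goes. What does not stand is giving the acronym for the same drugs a different label.

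The listing in SAP 20.10 shows verbatim components, coded terms and dates, so any misclassified patient can be found. First-line category is not among the efficacy subgroups in SAP 11.4, 20.6.2, 20.8.2 or 23.1.2. Both points stand and keep the matter small.

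Four stronger readings are tempting and are not supported:

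- A reader might infer that R-CVP is always counted as R-CHOP. It is not: the acronym, which neither document defines, goes to non-R-CHOP. Only entry by drug name fails.
- A reader might infer that the R-EPOCH labelling inflates the share given an anthracycline. R-EPOCH contains one, so that share is unchanged.
- A reader might put an error of several points on the table. No regimen counts are given. Protocol 1.2 calls anthracycline-based R-CHOP-like regimens the standard, and Protocol 6.7 asks only for DLBCL-specific therapies since the first DLBCL diagnosis. Both suggest few cases, possibly none.
- A reader might infer that the ORR or its comparison with the 20% monotherapy assumption is distorted. No efficacy analysis uses this variable.

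**Conclusion.** The point holds in limited form. As written, the R-CHOP drug-name search contradicts the section's own rule and sample entry, and it would tabulate an anthracycline-free four-drug regimen as R-CHOP when typed by drug name. The R-CHOP and equivalent rows also overlap without a priority, and equivalents typed by drug name are not recognised as such. The consequence is confined to one descriptive table and its listing, at about 1.25 points per affected patient. This rests on n = 80, on the extracted table text being complete, and on an unknown number of affected patients. The R-CHOP share is not always overstated: the net direction depends on which regimens were typed by name. No primary or secondary endpoint changes.

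**What to change.** In SAP 20.10:

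1. Require (`doxorub` or `hydroxydaun` or `adriamyc`) in the R-CHOP drug-name string, and put the vincristine alternatives in balanced parentheses. Balance the `CHP` string as well.
2. In the equivalent row, restrict plain `CHOP` to the non-rituximab antibody terms.
3. Add drug-name rules for the listed equivalents, such as the R-CHOP drugs plus etoposide, and obinutuzumab plus the CHOP drugs. Do the same for R-ACVBP and R-HyperCVAD, or state that these are assigned by review of the listing. Exempt the defining drugs, such as etoposide, from the rule that ignores added drugs.
4. State that the categories are mutually exclusive and are tested in the order equivalent, R-CHOP, non-R-CHOP. Step 1 alone leaves R-EPOCH by drug name in R-CHOP.
5. Check each assignment against the verbatim listing, and name the analysis set used as denominator.

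The cost is a few search terms, one sentence on order, and a rerun of one table and one listing. No new data are needed.

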20.11 Additional safety-related analyses
20.11.1 Listing of TEAEs summarized in as per Section 16.3.1

Listing for summaries outlined in 16.3.1

20.11.2 Opportunistic infections

TEAEs pertaining to the MedDRA CMQ "Opportunistic Infections" will be summarized by Primary SOC, HLT, PT and NCI-CTCAE Grade regardless of study treatment relationship

(based on the SAF). The PTs used to define the CMQ “Opportunistic Infections” are outlined in the APPENDIX.

A Listing will be provided displaying the TEAEs of the CMQ “Opportunistic infections” (based on the SAF).

20.11.3 TEAEs per patient years of exposure to MOR00208

Summary across both treatment phases:

Based on the SAF, the absolute number of TEAEs (i.e., the actual number of events) by patient years of exposure will be summarized by SOC, PT and NCI-CTCAE Grade. For the summary, patient years of exposure will be defined as follows:

$[(\text{end date of the MOR00208}) - (\text{start date of MOR00208}) + 1] / 365.25$.

The TEAEs per patient years of exposure will be reported with three decimal places.

Summary by treatment phase:

Based on the SAF, the number of TEAEs (i.e., the actual number of events) by patient years of exposure to combination treatment vs. MOR00208 monotherapy treatment will be summarized by SOC, PT and NCI-CTCAE Grade. Summaries will be provided separately for the combination treatment (MOR00208 + LEN) and MOR00208 monotherapy phase.

- Exposure to the combination treatment is defined as follows:

$[(\text{Latest date when at least one of either study drug has been discontinued}) - (\text{earliest date when the patient is treated with both study drugs}) + 1] / 365.25$.

Due to the fact that patients may discontinue LEN before reaching Cycle 12 Day 21 (i.e., the time when LEN is discontinued as per protocol), combination treatment may stop before completing 12 Cycles of LEN.

- Exposure to MOR00208 monotherapy treatment is defined as follows:

$[(\text{Discontinuation date of MOR00208}) - (\text{earliest date of MOR00208 infusion after LEN has been permanently discontinued}) + 1] / 365.25$.

Due to the fact that patients may discontinue LEN before reaching Cycle 12 Day 21 (i.e., the time when LEN is discontinued as per protocol), MOR00208 monotherapy treatment may start before reaching Cycle 13 Day 1. The TEAEs per patient years of exposure will be reported with three decimal places.

